Appendix III - Pain assessment) for each treatment phase:

- a. VelaShape III
- b. UltraShape Power
- 2. Clinical effects All visible and palpable immediate response will be recorded for the entire treatment area using a 4-point severity scale (Table 9).
- 3. Safety aspects will be assessed before and after each treatment:
 - a. Adverse Events Record the number, severity and type of any adverse event occurring before, during and after treatments.
- 4. Subject will also be provided with the following instructions for care of the treated areas in the informed consent form.
 - a. Temporary skin erythema (redness) and edema (swelling), as well as heat and tightening sensations, may occur up to a few hours after the treatment, but normally do not last longer. If the subject feels significant discomfort longer than that time, cool/cold compress (but not ice packs) may be applied for relief. Overthe-counter pain medication such as Tylenol may be used.
 - b. On the evening after the treatment, subjects should wash the treated areas gently with lukewarm water and avoid very hot or cold water in these areas. Generally, subjects may use their regular soaps after treatment, as long as these are not scrub soaps or exfoliants.
 - c. The treated areas should also not be exposed to potential mechanical damage (e.g., kickboxing, massage) at least 48 hours post-treatment.
 - d. Tanning of any sort (sun exposure, tanning beds, and artificial sunless tanning lotions) is not allowed in the treated areas during the entire course of the study since it might cause hyperpigmentation.
 - e. Subjects will be instructed to use a high factor sunscreen with SPF of at least 30 and to protect the treated areas from direct sunlight for the entire period of the study.

[figure not shown]
Return Visits

All subjects will be requested to return to the clinic at the following time-points during the study to assess the clinical performance of the device:

- Visit 4: FU1 4 weeks (±7 days) post last treatment.
- Visit 5: FU2 8 weeks (±7 days) post last treatment.
- Visit 6: FU3 12 weeks (±7 days) post last treatment.

At each return visit the following procedures will be conducted and data recorded:

Weight.

- Caliper measurements.
- Circumference measurements.
- Photographs as conducted at baseline visit.
- Completion of study questionnaires:
 - o Investigator satisfaction using the 5- Point Likert Scale.
 - Subject satisfaction using the 5- Point Likert Scale.
- Pregnancy inquiry prior to each treatment and at the final follow-up visit, a urine pregnancy test will be performed for women with child-bearing potential.

DATA ANALYSIS

Recording

All data will be recorded on site source documents and transcribed onto Case Report Forms (CRFs). The site will be monitored by Syneron staff or designees to assure adherence to the clinical trial requirements, subject safety, protocol procedures, and for data accuracy. The Case Report Forms and images will be reviewed and retrieved during the monitoring visit. All source documentation will remain in the subject's files at the site.

Review and Analysis of all data collected will be conducted by the Sponsor or designee as described for this protocol with the following data:

Demography and Baseline Measurements

Demographic and baseline/screening measurements (e.g., weight, height and digital images) will be collected and descriptively presented.

Treatment Visit

[figure not shown]
Skin assessment by the PI, photographs of the treated region, and pain scores will be collected used to document any adverse events to assess the device performance.

Follow-up Visit Measurements

Follow-up measurements for weight, circumference and digital images will be used for comparative measurements with their respective measurement at baseline. Primary endpoints will be evaluated 12 weeks post last treatment (Tx.3). Secondary endpoints may be evaluated at all visits.

Safety

Safety of device procedure will be evaluated through skin assessments by the PI and research staff. The occurrence and severity of all complications from the start of the study will be recoded.

Protocol Revisions and/or Deviations

Except for emergency situations, no changes or deviations in the conduct of this protocol will be permitted without the prior approval of the Sponsor.

The IRB/IEC that granted original approval for the study must be notified of all changes in the protocol, and will approve any change or deviation that may increase risk to the subject, and/or that may adversely affect the rights of the subject or validity of the investigation.

In the event of an emergency, the Investigator will institute any medical procedures deemed appropriate. However, all such procedures must be promptly reported to the sponsor and the IRB/IEC.

ADVERSE EVENTS (AE)

An adverse event (AE) is any adverse change in health or side effect that occurs in a study participant during their participation in the study.

Anticipated Adverse Effects

crusting)

Following treatment with the VelaShape III and/or UltraShape Power the following local adverse effects could occur (anticipated):

PurpuraHyperpigmentationBlisterHypopigmentation

➤ Bruising ➤ Soreness

2010116

BullaeFirst-degree burnErosionSecond-degree burn

Pain
Excessive skin redness (erythema)

> Damage to natural skin > Hair removal (pulling)

structure (scratching,

An adverse event (AE) is any undesired clinical occurrence in a study subject as indicated by signs, symptoms, illnesses, events that develop or worsen in severity in association with the study when deemed by the Investigator to be related to use of the device or study procedures. The Investigator will document all adverse signs and symptoms regardless of severity or frequency that are either volunteered by subjects or observed during the study that are related to the device. The Investigator will also record adverse experiences of subjects resulting from concurrent illnesses, reactions to concurrent medications, or progression of disease states that the Investigator deems related to the device. Included in the description will be the nature of the sign or symptom, the date of onset, whether the event was serious, the severity, the relationship

Confidential

Pilot Study to Evaluate VelaShape III & UltraShape Power Combined Treatment for Thigh Circumference Reduction

| Protocol # | DHF24451 | Rev. Date | October 6, 2017 | Page 29 of 39 |
|------------|----------|-----------|-----------------|-----------------------------|
| | | | | |

to study procedures or investigational device, the action taken, the date of resolution, and the outcome. The Principal Investigator will determine the relationship of the adverse device effect to the investigational device.

Unanticipated Adverse Device Effects

For device studies, part 21 CRF 812.3(s) uses the term unanticipated adverse device effect which is defined as any serious adverse effect on health or safety or any life-threatening problem or death caused by, or associated with the device, if that effect, problem, or death was not previously identified in nature, severity, or degree of incidence in the investigational plan or application (including a supplementary plan or application), or any other unanticipated serious problem associated with a device that relates to the rights, safety, or welfare of subjects.

Significant device failure may constitute an adverse event if an undesirable experience occurs. This definition includes any event resulting from insufficiencies or inadequacies in the instructions for use or the deployment of the device, or any event that is a result of a user error.

All unanticipated adverse effects will be graded as follows:

Mild: Sign or symptom, usually transient, non-life-threatening requiring no special

treatment and generally not interfering with usual activities.

Moderate: Sign or symptom, non-life-threatening which may be ameliorated by simple

therapeutic measures, and may interfere with usual activity.

Major: Sign or symptom that is intense or debilitating but non-life-threatening and

that interferes with usual activities. Recovery is usually aided by

therapeutic measures and the discontinuation of the study device may be

required.

Severe: Any untoward medical occurrence that at any time results in death or life-

threatening illness, resulting in persistent or significant disability/incapacity.

The relationship of the adverse effect to the study is defined as follows:

Probable: An adverse event has a strong temporal relationship to study device, and

another etiology is unlikely or significantly less likely.

Possible: An adverse event has a strong temporal relationship to the study device,

and an alternative etiology is equally or less likely compared to the

potential relationship to study device.

Confidential

| Protocol # DHF24451 Rev. Date October 6, 2017 Page 30 of 39 |
|---|
|---|

Probably not: An adverse event has little or no temporal relationship to the study device

and/or a more likely alternative etiology exists.

Not related: An adverse event has no temporal relationship to study device or has a much

more likely alternative etiology.

Reporting Adverse Events (AE) and Serious Adverse Events (SAE)

Anticipated Adverse Events: Anticipated adverse events in this study include Purpura, blistering, bruising, bullae, erosion, hyperpigmentation, hypopigmentation, soreness, pain, erythema, damage to natural skin structure and burn. If an unanticipated adverse event occurs at any time during or after the use of the VelaShape III and UltraShape devices, the Investigator must report it to Syneron.

The Investigator must report all unanticipated adverse device effects that are serious in nature to the clinical study monitor immediately or within twenty-four hours by telephone (see below). If such an unanticipated adverse device effect is reported after normal working hours, the Investigator will leave a voice message at the monitor's telephone number with accompanying report of the unanticipated adverse device effect emailed to the address below:

[name]., Clinical Consultant

Cell Number: [name] [contact]

E-mail: [contact]

A written report prepared by the Principal Investigator must follow within five working days to both the IRB and to Syneron Candela and should include a full description of the event and sequence.

Measures taken to protect the rights and welfare of subject

Research records will be available to study personnel, the sponsor, Ethics Review Committee and regulatory agencies as required. Research records may be used for purposes of medical education, after removal of subject names or other identifying information. In the ICF the subjects will be informed that the photographs and video taken of them during the study may be made available to the sponsor for marketing and instructional purposes, after removal of identifying information. All images collected will be stored without personal subject identifiers at the site and at Syneron.

Confidential

| Protocol # | DHF24451 | Rev. Date | October 6, 2017 | Page 31 of 39 |
|------------|----------|-----------|-----------------|-----------------------------|
| | | | | |

RISK/BENEFIT ANALYSIS

Risks

Syneron has determined that the *VelaShape III* and the *UltraShape Power* systems are non-significant risk devices. As indicated in the AE section, the anticipated risks associated with the use of both of the systems are:

Purpura

> Hyperpigmentation

Blister

> Hypopigmentation

Bruising

Soreness

Bullae

First-degree burn

Erosion

Second-degree burn

Pain

> Erythema

Hair pulling

Damage to natural skin structure (scratching, crusting)

Over 2,000 subjects worldwide participated in clinical research and underwent treatment with the different *VelaShape* or *UltraShape* devices. The *VelaShape III* and *UltraShape Power* devices that will be used in this study were previously used in clinical studies and emitted the same RF or acoustic energy, respectively. To date, no serious adverse events or unanticipated AEs have been reported. The reported AEs relate to skin and subcutaneous tissue confined to the treatment area and were all mild or moderate in nature and resolved within the study period.

Potential benefits to participating individuals and to society

Subjects may or may not benefit from circumference reduction, reduction of subcutaneous fatty tissue in the treated area via a non-invasive technique resulting in body contouring, or from skin laxity and texture improvement. All subjects in the treatment groups are expected to have some benefit from the treatment procedures as would be expected for the commercial devices (*VelaShape III* and *UltraShape Power*). Subject will receive all treatment procedures at no cost. This study will benefit the advancement of medicine by generating data on safety and efficacy that will aid in the development of an alternative treatment options to procedures with higher potential risks subjects, such as liposuction. The results of this study will help to determine whether this device is safe and effective for improvement of localized subcutaneous fat.

Conclusion:

Considering the potential benefits of non-invasive circumference and fat reduction relative to its risks, the potential benefits associated with the use of the VelaShape III and UltraShape Power Systems outweigh its risks, supporting study initiation.

ETHICS AND GOOD CLINICAL PRACTICE

This study will be carried out in compliance with the following:

- Syneron Standard Operating Procedures.
- Declaration of Helsinki, concerning medical research in humans (Recommendations Guiding Physicians in Biomedical Research Involving Human Subjects, Helsinki 1964, amended Tokyo, 1975, Venice 1983, and Hong Kong 1989).
- US Code of Federal Regulations (Title 21CFR including parts 50, 56 and 812 governing informed consent and IRB regulations).
- International Conference on Harmonization (ICH) Harmonized Tripartite Guideline for Good Clinical Practice (GCP), 1996.

QUALITY ASSURANCE AND STUDY MONITORING

Study Monitoring/Auditing/Inspection

The Study Monitor will be responsible for monitoring the study sites to review the data being collected. The sponsor shall implement and maintain quality control and quality assurance procedures with written standard operating procedures (SOPs) to ensure that the trial is being conducted and data are generated, documented and reported in compliance with the protocol, Good Clinical Practice (GCP) and applicable regulatory requirements. Visits will be made prior to the initiation of the study, at scheduled intervals throughout the study, and at termination of the study.

Once enrollment and treatments have begun, monitoring visits will take place more frequently pending enrollment and study activities.

The sponsor and site will maintain regular phone and e-mail correspondence throughout the study to confirm compliance of study procedures.

The investigator/institution agrees to allow the monitor and other authorized personnel direct access to source data/documents for trial related monitoring, the clinical supplies storage/dispensing area and to provide all documents in the Investigator Regulatory Binder for review, and to assist site auditors in their activities if requested. Requests by the Health Canada or regulatory agencies of other countries to inspect the study site may be made after adequate notification. The investigator may be required to assist the regulatory inspectors in their duties, if requested.

ADMINISTRATIVE PROCEDURES

Supply and Disposition of Study Device

If required the *VelaShape III* device, *UltraShape Power* device, and VelaSpray ease lotion, Parker Gel (coupling agents) will be supplied to the participating clinic. The device will be maintained by the Sponsor, as needed. Unused equipment or coupling agents will be returned to the Sponsor at the end of the study. At the end of all planned treatment sessions, the devices will be returned to Syneron Candela.

Control & Disposition of the Investigational Device

The *VelaShape III* and *UltraShape Power* devices will be used according to the instructions of the manufacturer, Syneron Medical Ltd. At the end of this study, any materials provided specifically for use in this study may be returned to the Sponsor, as described in the Clinical Trial Agreement and study budget.

Informed Consent

The Study Personnel will obtain written Informed Consent prior to the subject's participation in any study procedures. The Study Personnel will inform the subjects of the experimental procedure to be utilized and assure the subjects that their decision regarding participation in the study will have no bearing on the quality of medical care received and that their decision whether to participate in the study is strictly voluntary.

During the initial interview, the subject will be assured that they are free to change their mind and will be allowed to participate in the study or withdraw from the study with no adverse effect on their standard medical care.

Monitoring Plan

At least 3 monitoring visits are projected during the whole study. The frequency of which will be based on enrolment, study activities and the study visit scheduled. The first visit is scheduled at the initiation of the study prior to the first subject treatment in the study. The second visit is scheduled after enrolment and treatment has been initiated and a third visit will be for a close-out visit for the study. Interim visits may be conducted as needed to assure compliance to the study protocol and regulatory requirements. The number and frequency of monitoring visits may also be increased per the sponsor decision to collect data and images post treatment.

Case Report Forms

Paper case report forms will be used in this trial. All protocol-required information collected during the study must be entered in the appropriate field of the case report form (CRF). The

investigator, or designated representative, should complete the appropriate CRF fields as soon as possible after information is collected. The information must match the information that exists as source documents in the clinic chart, hospital chart, and/or investigator's files. An explanation should be given for all missing data.

It is the investigator's responsibility to assure the accurate completion, review, and approval of all CRFs and the timely completion and submission of all adverse event forms.

Record Maintenance

The investigator shall retain a copy of all study documents in accordance with the FDA regulations which specify that records should be kept for a period of two years: 1) following the date a marketing application either is approved or disapproved for the use, or 2) following notification to FDA that no application is being filed and/or that the study has been discontinued.

If an investigator leaves the study site before record retention obligations have expired, the sponsor should be notified in writing of the person designated to retain the study documents during and after the study.

Handling of clinical data. The data are entered into a secure database that only the sponsor has access to. Admission to the database requires access to a password-protected network secured by the Sponsor. This database is maintained by Syneron that performs backups, data verification, and application upgrades. All equipment housing the clinical data is located in locked rooms or a secure computer network. The only individuals, who view, extract and analyze data for protocol reports and publications are physicians and nurses who are members of the study team or Sponsors. Only authorized personnel of the Sponsors have access to databases.

Any paper copies of subject medical records or research records are stored in secure cabinets at the study site.

PUBLICATION POLICY

The investigator will not publish the study results and will not disclose confidential information received from Syneron without prior written agreement from Syneron. Such confidential information shall include any and all information relating to this study as described in the Clinical Trial Agreement. In the event that Syneron consents to the publication of data from this study, the investigator will provide Syneron manuscripts for review thirty days before submission for publication. Syneron will have no editorial rights over manuscripts. The investigator will also provide Syneron with advance notice of at least (30) days, of any presentation, lecture, abstract session, etc., in which any results from the study will be disclosed.

| SYNERON CANDELA | Pilot Study to Evaluate VelaShape III & UltraShape Power Combined Treatment for Thigh Circumference Reduction | | | | | |
|-----------------|--|----------|-----------|-----------------|-----------------------------|--|
| Confidential | Protocol # | DHF24451 | Rev. Date | October 6, 2017 | Page 35 of 39 | |

REFERENCES

- 1. Arner P. *OBESITY AND THE ADIPOCYTE, Regional adipocity in man*. Journal of Endocrinology (1997) 155, 191–192
- 2. Illouz YG, de Villiers YT. *Body Sculpturing by Lipoplasty*. Edinburgh: Churchill Livingstone, 1989.
- 3. Gasparotti M. Superficial liposuction: a new application of the technique for aged and flaccid skin. Aesthet Plast Surg (1992) 16, 141–53

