- 2. Number, severity and type of adverse events following combined treatment with the VelaShape III and UltraShape Power devices (immediate and delayed response), as recorded throughout the study.

Secondary Endpoints

- 1. Circumference reduction post combined VelaShape III and UltraShape Power treatments at Pre-Tx.2, Pre-Tx.3 and all follow-up visits (4wk FU, 8wk FU and 12wk FU) versus baseline. Statistically significant circumference reduction post combined treatment at the follow-up visits only.
- 2. Investigator satisfaction assessment will be performed independently, using a 5-point Likert scale questionnaire, at each follow-up visit (4wk FU, 8wk FU and 12wk FU).
- 3. Subject satisfaction assessment will be performed independently by the subject, using a 5-point Likert scale questionnaire, at each follow-up visit (4wk FU, 8wk FU and 12wk FU).
- 4. Comfort level during treatment: Comfort assessment will be performed independently by the subject using a 10-point NSR scale. The subjects will complete this questionnaire regarding each device separately and combined after each treatment (Tx.1, Tx.2 and Tx.3).

[figure not shown]
STUDY POPULATION

Number of Subjects

This study will enroll and be comprised of up to 40 subjects, who meet all the inclusion and none of the exclusion criteria, from up to two investigational sites. The subject will receive treatment for circumference reduction of thighs.

Subject Withdrawal and Replacement

Subjects enrolled in the study can discontinue their participation at any time for any reason without prejudice or reduction in the quality of their medical care. The investigators or sponsor can terminate a subject's participation in this study to protect the subject's health or if the subject fails to follow directions resulting in noncompliance to study procedures. Subjects who withdraw or are terminated from the study may be replaced to ensure at least 60 subjects have completed the study. Subjects who fail to complete the treatment may be replaced and will not be evaluable.

Inclusion Criteria

A subject is eligible to participate in the study if he/she meets all the following inclusion criteria:

- 1. Signed informed consent to participate in the study.
- 2. Female and male subjects, \geq 18 and \leq 60 years of age at the time of enrollment.
- 3. Fitzpatrick Skin Type I to VI.
- 4. Fat thickness of at least 1.5 cm (measured by calibrated caliper).

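### The protocol defines an adverse event twice, once regardless of cause and once only if judged related, and does not say which definition primary endpoint 2 uses

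*Combined protocol and SAP*

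**What the plan says.** The section ADVERSE EVENTS (AE) opens by defining an AE as "any adverse change in health or side effect that occurs in a study participant during their participation in the study". Cause plays no part in that definition.

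Under the sub-heading Anticipated Adverse Effects, after the list of local effects, the protocol defines the same term again. Here an undesired clinical occurrence is an AE "when deemed by the Investigator to be related to use of the device or study procedures". Two recording sentences follow:

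- The investigator documents signs and symptoms volunteered by subjects or "observed during the study that are related to the device".
- The investigator also records experiences arising from concurrent illness, reactions to other medication, or "progression of disease states that the Investigator deems related to the device".

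The same paragraph then asks that each event be described by, among other things, "whether the event was serious, the severity, the relationship" to study procedures or device.

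Primary Endpoint, item 2, reads "Number, severity and type of adverse events following combined treatment with the VelaShape III and UltraShape Power devices (immediate and delayed response"). It covers the whole study period and cites neither definition.

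**The concern.** Endpoint 2 is one of the two primary endpoints, and its unit of count is the adverse event. If the term has two meanings, the endpoint does too. Under the narrow text, the investigator decides on causality before anything is entered, and an event judged unrelated never becomes an AE record. The judgement then leaves no trace in the AE data for the sponsor, a monitor or a reader to check.

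An event correctly judged unrelated says little about the devices, so the loss in that case is small. The problem is that correct and incorrect judgements cannot be told apart once the record is absent. The study has one arm, so no control group is available against which to test an attribution. With up to two sites, each could follow a different paragraph, and their counts would not be comparable.

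**Working it through.** No formula applies: the plan states no AE rate, AE count or safety threshold to reproduce. The check is a comparison of every place that defines, records, grades or analyses AEs.

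**1. The two definitions.** The broad one includes any adverse change during participation. The narrow one adds a condition: the investigator must deem the event related to the device or study procedures. The narrow paragraph is also uneven within itself, because its definition covers device or procedures while its signs-and-symptoms sentence covers the device only. In its concurrent-illness sentence, the relatedness clause may qualify the whole list or only the last item. That gives two clear relatedness conditions and one ambiguous one.

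**2. What the rest of the protocol fits.**

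- Table 1, Safety Endpoints: any AEs recorded throughout the study, with no causality filter.
- Table 3, Safety row: relation to treatment is something recorded about an event, not a condition for recording it.
- Post-treatment Procedures, item 3: record any AE before, during and after treatments, with no filter.
- Relationship scale under Unanticipated Adverse Device Effects: four levels, including *Probably not* and *Not related*, each worded for an adverse event. Under the narrow definition these two levels would hold almost nothing; only procedure-related events with no link to the device could fall there.

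All four fit the broad definition. The signs-and-symptoms sentence under Anticipated Adverse Effects fits the narrow one.

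**3. Precedence.** No sentence says which definition governs. The DATA ANALYSIS section gives no rule either, such as separate tabulation of all AEs and related AEs.

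**4. Test cases** (illustrations, not events reported in the documents).

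- A burn in the treated area, judged device-related: an AE under both definitions.
- Irritation from shaving or taping, judged related to procedures but not to the device: an AE under both definitions, but outside the signs-and-symptoms sentence.
- An infection during follow-up, judged unrelated: an AE under the broad definition and not under the narrow one. Whether it is still written down depends on how the concurrent-illness sentence is read.

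**5. Size.** Let R be the number of events judged related and U the number judged unrelated. The broad count is R + U, the narrow count is R, and the share lost is U / (R + U). The documents give neither R nor U. The Risks section describes AEs in earlier studies in words only. The share cannot be computed, and no range is offered, since any figure would be invented.

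**The case against.** The strongest reply is that the narrow sentence is a mislabelled definition of an adverse device effect. It sits under Anticipated Adverse Effects, its paragraph closes on the relationship of the adverse device effect to the device, and the Glossary lists ADE separately from AE while the text never defines it. This is plausible, and it means that relabelling the sentence would resolve the conflict as well as deleting it. It does not remove the conflict, because the sentence as printed defines an adverse event in general terms and the paragraph goes on to concurrent illnesses and other medication.

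A second reply is that the reporting section already protects against loss. Under Reporting Adverse Events (AE) and Serious Adverse Events (SAE), an unanticipated adverse event at any time during or after device use must be reported to the sponsor, with no stated relatedness condition. This has weight: on the broad definition, an unrelated illness is not on the anticipated list and would have to be reported. But the duty is triggered by an adverse event, which is the disputed term, so it does not settle the matter.

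Third, this is a one-arm pilot, and endpoint 2 has no comparator, threshold or stated test. That stands: no inferential result changes.

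A reader might infer that unrelated events will go unrecorded, or that the sponsor will never learn of them. The documents do not support that. Table 3, the post-treatment instruction and the reporting duty all point towards recording, and local events may also be traceable through skin assessments and photographs. What is shown is that a site could follow the narrow text and comply with it.

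**Conclusion.** The protocol contains two incompatible definitions of its primary safety unit and no rule for choosing between them. The balance of the text favours the broad definition, but a site following the narrow paragraph as written would filter endpoint 2 before recording. This should be fixed. The conclusion rests only on the wording, and the numerical effect is unknown.

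A reader might go further and infer that AE severity cannot be graded, or that the immediate-response data are unusable. The documents do not support either. The Adverse Events form named in Table 3 is not among them and may specify a scale. Three minor wording points remain, separate from the main conclusion:

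- The four grades are assigned to unanticipated effects and start at mild, although an unanticipated adverse device effect is defined as "any serious adverse effect on health or safety or any life-threatening problem or death" or a comparable serious problem. The word *unanticipated* in the grading sentence may be a slip.
- *Severe* is simply the top level of Table 9, but in the four-grade scale it means death, life-threatening illness or lasting disability.
- Erythema is an expected side effect in the UltraShape procedure, an anticipated adverse effect as "Excessive skin redness (erythema)", and an anticipated AE without that qualifier in the reporting section. Whether an expected immediate response also counts as an AE is not stated.

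**What to change.** 1. Keep the opening definition in ADVERSE EVENTS (AE) as the single AE definition, and cite it in Primary Endpoint, item 2.
2. Under Anticipated Adverse Effects, delete the second definition sentence or relabel it as the definition of an adverse device effect (ADE).
3. Remove the relatedness conditions from the two recording sentences in that paragraph. This also removes the ambiguity about concurrent illnesses.
4. Record relatedness for every AE on the existing four-level scale.
5. Add a line to DATA ANALYSIS, Safety: tabulate all AEs, with device-related AEs as a subset.

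The minor points on severity wording and immediate responses can be reconciled in the same edit; the sponsor chooses the labels.

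The cost is wording edits in one paragraph, a citation in the endpoint, a line of analysis text and a check that the AE form agrees. Somewhat more events will be recorded (the number is unknown), and the total may look less favourable. The related subset keeps the device-specific figure visible. No treatment procedure or visit changes.
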